The typical treatment of PJ pneumonia is TMP-SMX is 2 DS tablets every 8 hours for 21 days. Higher concentrations of TMP-SMX are needed to treat the cyst form found in PJ pneumonia. For colonized patients who carry the vegetative form of PJ, a standard dose of TMP-SMX is more appropriate and less likely to cause side effects and potential discontinuation. As such the dose to be used for this study is 1 DS Q12H for 10 days. TMP-SMX is a large tablet which is difficult to over-encapsulate for blinding purposes. As such, the Research Pharmacy will supply a TMP-SMX suspension in individual dose syringes or a matching placebo in individual dose syringes for this study. A single syringe for TMP-SMX will contain 160 mg of trimethoprim and 800 mg of sulfamethoxazole, the same amount found in one DS tablet of TMP-SMX. If the patient is discharged prior to completing the 10-day course of the medication, they will be sent home with the remaining days of study medication and a medication diary which ~~IRB NUMBER: 2022-02~~ ~~IRB NUMBER: 2022-02~~ will be collected at the end of therapy visit. Standard operating

procedures used for all clinical trials within the Infectious Diseases Clinical Trials Unit will be followed at discharge including appropriate instruction of the patient on medication use, filling out the medication diary, when to contact the study staff, and making appointments for follow up.

When a patient with PJ pneumonia is hypoxic, the treatment of the PJ in addition to TMP-SMX includes steroids. This is done to minimize the inflammation from the β -D-glucans of PJ that are released when PJ is killed by TMP-SMX. It is unclear if steroids would be needed with the lower expected levels of PJ in the AECOPD patients but, since most patients with AECOPD are treated with steroids in any case, we feel it is safer to only include patients receiving steroids, hence the inclusion requirement of steroid use.

Evaluations

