Upon consent patients will be given the COPD Assessment Test (CAT) (<https://www.mdcalc.com/copd-assessment-test-cat>), a validated scoring system used in COPD patients to assess progression, functional status, and effectiveness of pulmonary rehabilitation.[29–32] Participants will be monitored daily while in the hospital for highest oxygen need, need for non-invasive or invasive mechanical ventilation, and adverse events, daily monitoring will be carried out by the nurse coordinator. Medications used for the treatment of COPD and antibiotics used will be collected retrospectively for each patient. If the patient remains hospitalized at end of therapy, 30 days, or 90 days then follow up will occur in the hospital. Otherwise, the patient will be asked to come to the Infectious Diseases Clinical Research Office for follow up visits at end of therapy (+0-3 days to allow for schedule issues and end of therapy falling on a weekend), 30 days +/- 5 days, and 90 days +/- 10 days. A \$30 stipend will be paid to the participants after each follow up visit. At the end of treatment visit, the medication diary will be collected. At each follow up visit, the nurse coordinator will review the patient's need for oxygen, their medications for the treatment of COPD, any need to see a physician or go to an urgent care or an emergency room for COPD, and any admission to the hospital for COPD. The CAT will be administered at each follow up visit. An expectorated sputum sample will be collected at each follow up visit which will be transported to the Infectious Diseases Research Laboratory for analysis; sputum samples will be processed and analyzed with the Unyvero LRT system for presence of PJ by PCR. The schedule of events for

[figure not shown]

Figure 1: Schedule of Events

the study is shown in figure 1.

Statistical analysis

No formal power analysis was performed, the sample size of 15 patients per arm is felt to be appropriate for a pilot study and appropriate to the funding for this application. We expect to find enough cases of PJ colonization to identify and recruit the 30 patients to be included in the study from the pool of patients for the EPIC study.

Time to return to baseline O2 requirements, and time to next admission for exacerbation will be analyzed using cox proportional hazards regression or other ~~more appropriate time~~ time-to-event analysis method. Need for mechanical

IRB APPROVAL DATE: 06/08/2022

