ventilation will be analyzed using logistic regression. LOS will be analyzed using quantile regression. The number of urgent care/emergency room visits and number of hospitalizations for AECOPD within 3 months and mortality will be analyzed using Poisson regression (or other appropriate method if there is evidence of overdispersion). Durability of decolonization, change in medications for COPD, and CAT score will be a longitudinal analysis. This analysis plan was developed by [name] in Biostatistics who will perform the analysis.

Any participants who withdraw prior to the EOT assessment will be dropped from the study and replaced. Any participants who withdraw after completing the EOT assessment will be analyzed in a modified intent to treat population and not replaced. Only participants who complete all assessments will be analyzed as per protocol.

Anticipated Outcomes

We anticipate treatment of PJ colonized AECOPD patients with standard of care plus TMP-SMX will improve symptoms, decrease LOS and increase the interval free of acute exacerbations above standard of care alone. Using the CAT, we expect to have a quantifiable score which can demonstrate a difference in outcomes between the two groups.

We also anticipate that patients with AECOPD who are colonized with PJ and treated with standard of care alone will maintain colonization over the 3-month period of follow up. Patients who are treated with TMP-SMX in addition to standard of care are expected to have microbiological eradication of PJ colonization and we expect that eradication to last through the 3-month follow up visit.

Potential problem areas and alternative tactics

This study is relatively simple and straight forward, we do not anticipate any issues with identifying or recruiting patients for the study but recognize that recruitment can be lower than expected for any study.

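### The 3-month visit and admission counts have no exposure term, so time lost after post-EOT withdrawal or death is treated as event-free

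*Combined protocol and SAP*

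**What the plan says.** All references are to the combined protocol and SAP.

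- **Model (Statistical analysis).** "The number of urgent care/emergency room visits and number of hospitalizations for AECOPD within 3 months and mortality will be analyzed using Poisson regression". The stated fallback is "or other appropriate method if there is evidence of overdispersion". No offset, rate, person-time or risk period is mentioned.
- **Who is analysed (Statistical analysis).** "Any participants who withdraw prior to the EOT assessment will be dropped from the study and replaced". By contrast, "Any participants who withdraw after completing the EOT assessment will be analyzed in a modified intent to treat population and not replaced". The per-protocol set is limited to patients with every assessment done.
- **Timing (The Intervention; Evaluations).** "the dose to be used for this study is 1 DS Q12H for 10 days", and the EOT visit may fall up to 3 days later. The later visits are at "30 days +/- 5 days, and 90 days +/- 10 days".
- **How events are found (Evaluations).** For events due to COPD, the nurse coordinator reviews at each follow-up visit "any need to see a physician or go to an urgent care or an emergency room for COPD, and any admission to the hospital for" this disease. No other route for finding events after discharge is described.
- **Deaths.** Mortality is an outcome in the same sentence as the counts, but no rule says how a death affects a patient's visit and admission counts.

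**The concern.** A Poisson model of a count with no exposure term assumes that every patient was observed for the same time. Here the plan's own retention rule breaks that assumption. A patient who leaves just after the EOT visit has 10 to 13 days of observation and stays in the analysis beside patients followed for 90 days. If that patient had no event in those days, the data show zero events over 3 months. A patient who dies at day 20 is handled the same way.

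The overdispersion fallback does not help. It changes the standard error and leaves the unequal exposure where it was.

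The plan is also uneven on this. Time to next admission is to be analysed by Cox regression or another time-to-event method, which can censor a withdrawal. The count of the same admissions has no equivalent, so one patient could be censored in one analysis and scored as event-free in the other.

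The estimates from this pilot are meant to inform larger trials, so a shift in the rate ratio matters even where no test is significant.

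**Working it through.** The plan states no event rate, dropout rate or power, so it has no figure to reproduce. The check asks what ratio to expect from counts without an offset when treatment has no effect.

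**Inputs from the documents:** 15 per arm, with a fallback of 10 per arm (Potential problem areas and alternative tactics); earliest retained withdrawal at about day 10 to 13; nominal follow-up of 90 days.

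**Assumptions:** days run from the start of treatment, the event rate is constant and equal in both arms, and losses occur on a common day t. The number and timing of losses are illustrative.

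**Formula.** With k1 and k0 losses in arms of size n, the expected count ratio equals the ratio of mean follow-up:

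ratio = [(n − k1)·90 + k1·t] / [(n − k0)·90 + k0·t]

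**Results, true ratio 1.00:**

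| n per arm | Losses | t = day 10 | t = day 50 |
|---|---|---|---|
| 15 | 3 vs 0 | (12·90 + 30)/1350 = 0.82 | (12·90 + 150)/1350 = 0.91 |
| 15 | 4 vs 1 | 1030/1270 = 0.81 | 1190/1310 = 0.91 |
| 15 | 2 vs 2 | 1.00 | 1.00 |
| 10 | 3 vs 0 | (7·90 + 30)/900 = 0.73 | (7·90 + 150)/900 = 0.87 |

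For loss at day 13 with none in the other arm and 15 per arm:

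- 1 loss: 1273/1350 = 0.94
- 2 losses: 1196/1350 = 0.89
- 3 losses: 1119/1350 = 0.83
- 4 losses: 1042/1350 = 0.77

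Equal losses leave the ratio alone but still lower the counts. With 2 vs 2 at day 13, mean follow-up is 1196/15 = 79.7 days, so both arms read about 11% low.

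**Simulation.** This used 20,000 trials per scenario, 15 per arm, an assumed 0.5 events per patient per 90 days, and loss days uniform from 10 to 80.

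| Losses | Ratio, no offset | Ratio, with offset |
|---|---|---|
| 3 vs 0 | 0.90 | 1.00 |
| 4 vs 1 | 0.90 | 1.00 |
| 3 vs 1 | 0.93 | 1.00 |
| 2 vs 2 | 1.00 | 1.00 |

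Across all scenarios, rejection under the null was 3.2–3.7% without the offset and 2.9–3.4% with it, against a nominal 5%.

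**Visit window.** The last visit is at "90 days +/- 10 days". If events were counted up to the visit, two completers could differ by 100/80 = 1.25 in exposure. With a 3-month limit taken as day 90, only those last seen before day 90 are short, by at most 10/90 = 11%.

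**The case against.** The strongest reply is that the plan is silent rather than wrong. An offset is a routine part of Poisson regression, and nothing in the text rules it out. A reader might infer that the sponsor chose to model raw counts; the documents do not say so. But the same text defines the outcome as a number within 3 months and retains patients with far less follow-up. Silence there leaves the flawed reading open.

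Other parts of the reply limit the point:

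- **Drug intolerance.** A reader might expect intolerance to drive unequal dropout. Withdrawals during the 10-day course fall before the EOT visit and are dropped and replaced, so they mostly do not reach these counts. What remains is later loss and death, in a double-blind trial, with no stated reason for the arms to differ. An imbalance of a few patients can still arise by chance with 15 per arm.
- **Visit window.** The 25% spread depends on counting to the visit date, which the 3-month definition argues against. The remaining shortfall is small and likely to balance between arms.
- **Other analyses.** The time-to-event analysis can censor withdrawals, but it covers only the next admission. The per-protocol set avoids most of the problem only by leaving out deaths and withdrawals. Neither repairs the modified intention-to-treat counts.
- **Deaths.** Patients expected to live less than 3 months are excluded, which should limit truncation by death without removing it.
- **Precision.** At 0.5 events per patient (7.5 per arm), the standard error of the log ratio is √(1/7.5 + 1/7.5) = 0.52. The log bias at 0.83 is 0.19, about a third of that. This is a pilot with no power claim, so chance error outweighs the bias. The bias is nevertheless avoidable.

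**Conclusion.** The point holds as a gap in the analysis method. As written, the count analysis has no exposure term while the analysis set includes patients with as little as 10 to 13 days observed. Counts are understated whenever patients are lost or die after the EOT visit. The rate ratio is biased only when that loss differs by arm, and then in favour of the arm with more of it.

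The size is illustrative: 0.82 to 0.91 for 3 versus 0 losses at 15 per arm, 0.73 to 0.87 at 10 per arm, and 1.00 for equal losses. These figures rest on a constant event rate and assumed loss patterns, since the documents supply neither rate nor pattern.

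A reader might infer that the omission inflates false-positive findings. The simulated rejection rates do not support that. The damage is to the point estimate and the reported event rates.

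**What to change.** In the Statistical analysis section:

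1. Include log(observed days at risk) as an offset in the Poisson model, or in whatever model replaces it for overdispersion.
2. End the risk period at the earliest of day 90, withdrawal or last contact, and death. Count only events inside it.
3. Start the risk period at index discharge for readmissions and outpatient visits, because a patient still in hospital cannot have either, or justify starting at randomisation. The choice needs a sentence, because length of stay is itself an outcome the sponsor expects treatment to change. State how patients never discharged within the period are handled.
4. Report events and person-time by arm, with the number and timing of withdrawals and deaths.
5. Add a simple sensitivity analysis, for example one that treats death as an unfavourable event rather than as censoring.

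The cost is a few lines of text, one model term and the recording of discharge, last-contact and death dates. The change has one small downside: the offset assumes that loss is unrelated to event risk, which is doubtful for deaths in this population. Item 5 is there for that reason.

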
• Carries the diagnosis of COPD and admitted for and admitted with AECOPD to Beaumont, Royal Oak
• AECOPD requires increased cough, increased sputum production, and shortness of breath +/- increased oxygen needs from baseline• Able to produce a sputum sample• Men or women, age ≥40 and <90• Previously enrolled in the EPIC study and PJ detected in their sputum• Currently treated with steroids• Kidney function not severely impaired ($\text{CrCl} \geq 60$)• AST and ALT $\leq 5x$ Upper limit of normal• Willing and able to provide consent to the study	
• Currently diagnosed with pneumonia or COVID• Allergy or hypersensitivity to TMP-SMX• Current ICU admission or mechanical ventilation• Active cancer or chemotherapy (except non-melanoma skin cancer)• Other potentially confounding pulmonary diagnosis• HIV, leukopenia, neutropenia or other immunosuppressive condition or current use of immunosuppressive medications• Presence of gastrointestinal tract abnormalities that would prevent absorption of medications• Patients with concomitant infection requiring antibiotics active against PJ• Concomitant use of coumadin, phenytoin, pioglitazone, repaglinide, rosiglitazone, glipizide or gliburide• Megaloblastic anemia due to folate deficiency• Pregnancy• Expected life span less than 3 months

Table 1: Inclusion/Exclusion Criteria

3 attending physicians, 3 fellows, and 2 residents available to consent. In addition, a nurse coordinator experienced at consenting will be available to consent or assist the physicians with consenting in order to further educate physician trainees who are sub-investigators on this study. Given physician time commitments we expect the nurse may perform a majority of the consenting herself. Patients who consent for participation will be randomized in a 1:1 ratio to one of two groups.

Group #1 – Fifteen patients will receive a suspension with the equivalent of one DS TMP-SMX by mouth every 12 hours.

Group #2 – Fifteen patients will receive a suspension with placebo by mouth every 12 hours.

Randomization will be generated by biostats and sealed envelopes will be held by [name] in the Research Pharmacy to be opened when a patient is recruited. [name] is the only one who will be unblinded and, in case of an emergency, he can break the blind at the request of one of the attending physician investigators.

The Intervention

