By identifying patients colonized with PJ in the EPIC study, we will carry the cost of screening for the TOPIC study in the EPIC study, which allows the funding for this study to bear other needed expenses and make it feasible. The key personnel for the EPIC study overlap completely with the TOPIC study. We aim to enroll 30 patients but if we will have difficulties in recruiting, we may need to decrease the number of patients in the treatment group to 10 in each arm. Having a stipend for follow up visits will help with recruitment as will having [name], the director of Pulmonary Rehabilitation, as an investigator.

It is possible that we may see clinical improvement in the TMP-SMX group without microbiologic eradication. This could be due to TMP-SMX incompletely killing the PJ, we could have chosen a sub-optimal dose for the study, or it could be that the high sensitivity of PCR and the ability to detect dead organisms will work against us and we could still detect the organisms even if all were killed. Checking for colonization again at 30 days and at 90 days may be able to reveal this as dead organisms are cleared from the respiratory tract. It may be that it will take a longer trial to actually show microbiologic clearance even in the setting of clinical benefit.

This is a pilot study and, since we will have a small number of patients, we may not be able to detect statistically significant differences between the two groups, however by selecting the known PJ colonized patients for the study we are increasing the chances of being able to show a difference between the groups.

Potential for continuing this study with additional extramural funding

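### Mortality, which can occur only once per patient, is put in a Poisson model meant for counts, so its standard error is somewhat too large and the overdispersion clause does not correct it

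*Combined protocol and SAP*

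**What the plan says.** In the combined protocol and SAP, the Statistical analysis section names one method for three outcomes: urgent care or emergency visits, AECOPD hospitalizations, and death. Of these it says "within 3 months and mortality will be analyzed using Poisson regression". The only stated way out is "or other appropriate method if there is evidence of overdispersion". For mortality the section gives no follow-up-time offset, variance estimator, exact method or time point.

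The other yes/no outcome in the same paragraph, mechanical ventilation, is treated differently: "ventilation will be analyzed using logistic regression".

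On size, the section says "the sample size of 15 patients per arm is felt to be appropriate for a pilot study" and "No formal power analysis was performed". Under Potential problem areas and alternative tactics, slow recruitment may "decrease the number of patients in the treatment group to 10 in each arm". Allocation is 1:1.

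**The concern.** Visits and admissions can recur, so a Poisson model with a check for extra variation suits them. A patient dies at most once. A 0/1 variable with mean p has variance p(1-p), whereas Poisson assumes p, so the model-based interval for the mortality ratio is too wide. Someone reading the overdispersion clause could think it protects all three outcomes. For 0/1 data the departure runs the other way, towards too little variation, and the clause does not cover that.

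At stake is the width of the mortality interval in a very small trial whose results are meant to inform the design of larger ones.

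**Working it through.** **Inputs.** From the documents: n = 15 per arm, fallback 10 per arm, 1:1 allocation, Poisson regression. Assumed, because the documents are silent: mortality of 5% to 40%, two-sided 5% level, and a model containing treatment arm only. The plan states no figure on this point, so there is none to reproduce.

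**Standard error.** With d1 and d2 deaths among n per arm, both at least 1:

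- Poisson, model-based: SE(log RR) = sqrt(1/d1 + 1/d2)
- Binomial (the sandwich variance gives the same): SE(log RR) = sqrt(1/d1 + 1/d2 - 2/n)
- With equal observed risk p, the ratio of the two is 1/sqrt(1-p)

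At n = 15:

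| Deaths | Poisson SE | Binomial SE | Ratio | 95% CI for RR 0.50, Poisson | Same, binomial |
|---|---|---|---|---|---|
| 2 v 4 | sqrt(0.750) = 0.866 | sqrt(0.750 - 0.133) = 0.785 | 1.103 | 0.09 to 2.73 | 0.11 to 2.33 |
| 3 v 6 | sqrt(0.500) = 0.707 | sqrt(0.500 - 0.133) = 0.606 | 1.168 | 0.13 to 2.00 | 0.15 to 1.64 |

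Averaging the ratio over all tables with deaths in both arms, by exact enumeration with equal true mortality:

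| Assumed mortality | 1/sqrt(1-p) | Mean ratio, 15 per arm | Mean ratio, 10 per arm |
|---|---|---|---|
| 5% | 1.026 | 1.046 | 1.065 |
| 10% | 1.054 | 1.062 | 1.079 |
| 20% | 1.118 | 1.111 | 1.122 |
| 30% | 1.195 | 1.184 | 1.187 |

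At low rates the mean ratio exceeds the formula because requiring a death in each arm raises the observed proportion.

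**Overdispersion clause.** In an arm-only Poisson fit to 0/1 data, an arm with d deaths (d at least 1) contributes n - d to the Pearson chi-square, and an arm with none contributes 0. With deaths in both arms, Pearson/df = [(n - d1) + (n - d2)]/(2n - 2). The largest value, at 1 v 1, is (2n - 2)/(2n - 2) = 1. For 2 v 4 at n = 15 it is 24/28 = 0.86, and for 3 v 6 it is 21/28 = 0.75. Over every possible table the maximum is 1.00 at both 15 and 10 per arm. Deviance/df is at most 0.785 and 0.814 respectively.

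**Effect on the test.** At an assumed 10% v 40% mortality and 15 per arm, power over all trials is 8.3% (Poisson Wald) v 14.4% (binomial Wald). No finite ratio exists in the 21% of trials with an arm without deaths, and these count as non-rejections. Among the remaining trials the figures are 10.5% v 18.1%. With equal mortality of 20%, type I error is 0.12% v 0.35%.

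**An arm with no deaths.** The probability is 1 - [1 - (1-p)^n]^2. At 15 per arm this is 71% at p = 5%, 37% at 10% and 7% at 20%. At 10 per arm it is 84%, 58% and 20%. With 0 v 2 deaths at 15 per arm, a fitted Poisson model returned a model-based SE of about 11,459 and a spurious robust SE of 0.71. The Newcombe interval for the risk difference of -0.13 is -0.38 to 0.09.

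**The case against.** The strongest reply is that the plan never says mortality is to be analysed as a proportion. Poisson regression of deaths on follow-up time is a standard rate model, and patients who withdraw after end of treatment stay in the modified intent-to-treat population with shorter follow-up. With a person-time offset the standard error would not be too wide. Pearson/df would then be above 1 almost always (at least 99.9% of simulated trials with deaths in both arms). Likewise, Poisson with a sandwich variance is a common analysis of binary outcomes and is compatible with the sentence. This reply stands in part: the finding depends on a plain yes/no comparison by arm. It does not clear the plan, which states neither an offset nor a robust variance.

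A reader might infer that the clause can never be triggered under any model. The documents do not support that. Besides the offset case, adding an unrelated continuous covariate pushed Pearson/df above 1 by chance in 34% of simulated trials at 5% mortality, falling to 1% at 30%, although deviance/df never exceeded 1. The plan names no covariates.

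A reader might also infer a serious loss of power. The 10% v 40% scenario is extreme for a population that excludes intensive-care and ventilated patients and those not expected to survive 3 months, and no power is claimed in any case. With equal mortality of 20% the two standard errors disagree on significance in only 0.2% of trials, and both example pairs of intervals include 1. The binomial Wald interval is itself very conservative at this size, so much of the width comes from few deaths rather than from the Poisson variance.

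Finally, mortality is not among the outcomes listed in the summary or under Specific Aims, and the protocol itself warns that differences may not be detectable. That keeps the point minor.

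**Conclusion.** The point holds as a small error in the stated method. For deaths compared by arm as a yes/no outcome, with model-based variance and no offset, the standard error of the log risk ratio is too large by about 5-6% at assumed mortality of 5-10%, 11% at 20% and 18% at 30% (15 per arm, deaths in both arms). The overdispersion clause cannot repair this in an arm-only model.

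The direction is conservative, so nothing here suggests false claims of benefit or harm. The documents give no mortality rate, so the size cannot be fixed more closely. At low rates the likelier practical failure is an arm with no deaths, where the planned ratio is not estimable at all. The sentence remains adequate for the two count outcomes.

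**What to change.** Take mortality out of the Poisson sentence. Report deaths by arm to the day-90 visit with a risk difference and a Newcombe or Miettinen-Nurminen 95% interval, which stays finite when an arm has no deaths. A robust variance alone would not achieve that. If a risk ratio is also wanted, use a binomial or robust variance and only where both arms have deaths. Keep Poisson and its overdispersion clause for the visit and hospitalization counts. If a death rate over follow-up time was intended, state the person-time offset instead.

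The cost is one sentence, with no extra patients. There is a small downside: a proportion at day 90 needs vital status to be known for each patient, or the number unknown reported by arm. The plan should also say that a death before the end-of-treatment assessment counts as a death, since it does not say whether such a patient falls under its rule to drop and replace early withdrawals.

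### Does the plan need to say how the consent CAT score enters the longitudinal analysis?

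*Combined protocol and SAP*

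**What the plan says.** Under Evaluations, the CAT is given once consent is obtained. The follow-up visits are at end of therapy and at "30 days +/- 5 days, and 90 days +/- 10 days", and "The CAT will be administered at each follow up visit". Under Patients, "Patients who consent for participation will be randomized in a 1:1 ratio to one of two groups". A score taken at consent therefore reads as a pre-randomisation measure. The schedule-of-events figure is not reproduced, so this order is inferred from the text.

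The Statistical analysis section disposes of the CAT in one sentence, shared with two other outcomes: "Durability of decolonization, change in medications for COPD, and CAT score will be a longitudinal analysis". It names no covariate, contrast, visit or covariance structure. On size it says "No formal power analysis was performed, the sample size of 15 patients per arm is felt to be appropriate for a pilot study", and the section on potential problems adds that "we may need to decrease the number of patients in the treatment group to 10 in each arm". Under Anticipated Outcomes the authors write of the CAT that "we expect to have a quantifiable score which can demonstrate a difference in outcomes between the two groups".

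**The concern.** A longitudinal analysis describes a data structure, not a model. Two of the models it allows are usually inefficient in a randomised trial. One compares follow-up scores and ignores the consent score. The other treats the consent score as the first repeated outcome with its own mean in each arm and tests arm-by-time; with complete data that is a change-from-baseline comparison. Conditioning on the baseline score, or constraining the arms to a common baseline mean, is generally more precise and uses data the trial collects anyway.

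With 15 patients per arm, perhaps 10, lost precision matters, and the authors single out the CAT as a measure that could separate the groups. Leaving the model open also leaves room to choose it after seeing the data.

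**Working it through.** **Inputs.** From the documents: 15 per arm, with 10 as the fallback; one consent score; three follow-up scores. The plan states no CAT standard deviation, effect, correlation or power, so there is no figure to reproduce. Assumed: equal SDs at all visits (set to 1) and a baseline/follow-up correlation ρ from 0.1 to 0.7.

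**Single visit.** Variance of the arm difference, relative to follow-up only (= 1), with n per arm:

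- Change from baseline: 2(1 − ρ)
- Adjusted for baseline: (1 − ρ²) × k, where k = 1 + 1/(2n − 4) allows for estimating the slope. For n = 15, k = 1 + 1/26 = 1.038. For n = 10, k = 1 + 1/16 = 1.0625.

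| ρ | Change | Adjusted, n = 15 | Adjusted, n = 10 |
|---|---|---|---|
| 0.1 | 1.80 | 1.028 | 1.052 |
| 0.2 | 1.60 | 0.997 | 1.020 |
| 0.3 | 1.40 | 0.945 | 0.967 |
| 0.5 | 1.00 | 0.779 | 0.797 |
| 0.7 | 0.60 | 0.530 | 0.542 |

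Simulation with 20,000 trials per setting agrees: at n = 15 the adjusted values were 1.028, 0.947, 0.779 and 0.526 for ρ = 0.1, 0.3, 0.5 and 0.7.

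**Break-even.** Against follow-up only, adjustment gains when ρ exceeds √(1 − 1/k), which is 0.19 at n = 15 and 0.24 at n = 10. Against a change score it gains when ρ is below 2/k − 1, which is 0.93 and 0.88.

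**Interval width.** The 95% half-width is t × √(2 × factor / n). At n = 15, in SD units:

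- ρ = 0.3: 0.748 follow-up only, 0.885 change, 0.728 adjusted
- ρ = 0.5: 0.748, 0.748, 0.661
- ρ = 0.7: 0.748, 0.579, 0.545

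For a true difference of 0.75 SD, power is about 51% follow-up only and 53% adjusted at ρ = 0.3, and 51% and 61% at ρ = 0.5.

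**What a one-line addition would do over three visits.** The obvious sentence would list arm, visit, arm-by-visit and baseline CAT. That forces one baseline slope β on all visits, and the large-sample relative variance at visit v becomes 1 + β² − 2βρᵥ. The single-visit formula above no longer applies. If correlations fall over end of therapy, day 30 and day 90:

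- At 0.7, 0.5, 0.3, the ordinary least-squares slope is their mean, 0.5, so day 90 gives 1 + 0.25 − 0.30 = 0.95. A generalised least-squares slope, with an assumed correlation of 0.7 between follow-ups, is 0.682 and gives 1.06.
- At 0.6, 0.4, 0.1, the mean slope is 0.367 and day 90 gives 1 + 0.134 − 0.073 = 1.06. The generalised slope of 0.635 gives 1.28.

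So a plausible but hasty specification could be 6% to 28% worse at day 90 than ignoring baseline. With a milder decline (0.5, 0.4, 0.3) it gains at every visit. A baseline-by-visit term, or a common-baseline model, avoids the problem. The baseline-by-visit version costs one slope per visit, three in all.

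**Level of detail elsewhere.** The same section gives each other outcome a method family only (Cox, logistic, quantile or Poisson regression), with no covariates or contrasts. The CAT is treated like the rest.

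**The case for a change.** The strongest case for a change is that it is nearly free. A sentence or two would fix the model and one contrast, with no new data. With arms this small, chance imbalance at baseline is not negligible: the SD of the baseline arm difference is √(2/15) = 0.37 SD, or √(2/10) = 0.45 SD at the fallback size. Follow-up-only and change-score results can then diverge, and nothing says which would be reported. The change score is also at its worst where the correlation is low, which is plausible when baseline is taken during an exacerbation: its variance is 1.40 times follow-up only at ρ = 0.3. The data are meant to support grant applications and the design of a larger trial, where an estimate fixed in advance carries more weight.

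All of that stands as a reason why a clarification would be harmless and somewhat useful. It does not show a fault. Nothing in the plan points to ignoring or subtracting the consent score. A low correlation counts against the change score, but it also removes the gain from adjustment. And the useful sentence is less trivial than it looks, because the simplest version may lose precision at the last visit.

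**Conclusion.** The omission is real and the precision argument is right as far as it goes, but the plan does not need changing. What is missing is the choice of model within a family that already includes the efficient ones. With complete data each reading gives an unbiased comparison of randomised arms, so the stake is interval width and some analyst discretion on one of several Aim 1 outcomes. The trial has no primary outcome and no power calculation, and the plan itself warns that differences may not reach significance.

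The size is uncertain. At a single visit with 15 per arm, adjustment changes the variance against follow-up only by anything from a 47% reduction (ρ = 0.7) through about 5% (ρ = 0.3) to a 3% increase (ρ = 0.1; 5% at 10 per arm). This rests on equal SDs, on correlations the documents do not give, and on the consent CAT preceding randomisation. Choosing how baseline enters the model before unblinding is routine work for the biostatistician and needs no amendment.
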